
Sample size determination:
	
Fat Liver Content Change from Baseline:                  The current sample size of 40 subjects per group should yield approximately 85% power to detect a treatment effect of at least -5% with respect to the difference in the mean change from Baseline between one of the IMM-124E treatment groups and placebo assuming a standard deviation (SD) of 7.3% (<math>\alpha=0.05</math>; two-tailed; unpaired t-test). The SD of 7.3% for the change from Baseline endpoint was derived assuming 1) SDs of 6% for each timepoint, 2) equal variances in each treatment group and 3) a low to moderate correlation of 0.25 between pre- and post-Baseline measurements.
 
Sample size and power estimates have not been adjusted for multiple comparisons or multiple endpoints, dropouts or stratification.
 
The analysis of each primary endpoint will be based on a linear model that incorporates the baseline measure as a covariate, the stratification factor and randomized treatment group. Pairwise comparisons of each active treatment group to control will be conducted via linear contrasts.

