**APPENDIX G PROTOCOL AMENDMENT #3 – SUMMARY OF CHANGES**

## RATIONALE FOR PROTOCOL AMENDMENT No. # 3

This protocol amendment has been generated to achieve the following goals:

1. to improve recruitment by eliminating the ALT eligibility requirement and using ALT as a secondary endpoint instead of a primary endpoint
2. to allow for a planned interim analysis
3. to allow for MRI-based stratification
4. extend screening period from 28 days to 45 days to allow for better operational streamlining
5. to better clarify existing wording and phrasing issues within the protocol
6. correct typo and add administrative changes

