7.2 Primary efficacy analyses

The hepatic fat fraction will be summarised and tabulated for the Baseline and Week 24 visits along with change from Baseline by randomised treatment group. Change in hepatic fat fraction from Baseline will be analysed using analysis of variance on the ITT, PP and FAS populations, where the model will include the treatment group and another subgrouping variable. As determined by baseline values, hepatic fat fraction categories ($\leq 10\%$, $>10\% - <21\%$, $\geq 21\% - <30\%$ and $\geq 30\%$), HbA1c group ($< 6\%$ and $\geq 6\%$), and ALT (greater or less than 1.5 x the upper normal limit) will be used to subgroup the analysis populations. Further, data from liver biopsies up to 6 months prior to screening will also be used to subgroup analysis populations based on fibrosis (0-1 vs. 2-3), NAS inflammation (0-1 vs. 2-3), and NAS ballooning (0-1 vs. 2). These will be used in addition to the main effects factors and the two-way interaction of those main effects.

In the primary analysis, any missing data will remain missing. Treatment effects between placebo and each of the active treatment groups within each of the hepatic fat and HbA1c categories will be generated and tested for significant differences between treatment and placebo using pre-specified contrasts.

To examine the effect of treatment within the various levels of these subgroup variables, a mixed models ANOVA will be employed if there are an appropriate number of observations in each cell (created by the crossing of study treatment and subgroup categories) and the data does not differ significantly from a normal distribution. In the event that this is not the case, the data will be ranked in an attempt to normalise it, and pairwise contrasts between treatment groups will be performed using Wilcoxon rank sum tests within each combination of visit and subgroup variable level will be performed. However, if the ranked data is also not normally distributed, a permutation test will be employed whereby the unranked data will be randomly sampled (Lehmann, 2006). No adjustment for multiple testing will be made. See Appendix 1 for more information on both the Wilcoxon rank-sum test and the permutation test.

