7.3 Secondary efficacy analyses

The following analyses of secondary efficacy will be performed on the FAS population. However, if the results for the primary efficacy analysis differ across populations, the ITT and PP populations may also be subject to secondary efficacy analysis. For the analyses detailed in this section and section 7.4, inferential statistical analysis will be performed on the same basis as for the primary endpoint. For those values that are recorded at 3 or more time-points, the baseline value will be included in the repeated measures analysis as a covariate. For analyses with only a baseline and final value, t-tests or Wilcoxon rank-sum tests will be performed depending on the distribution of the data. In addition to this, the mean change from baseline for all relevant variables will be assessed and presented.

Serum concentrations of IMM-214E bovine antibodies (including but not limited to: maximum and minimum observed concentration, area under the concentration-time curve, and (if feasible) elimination half-life) will be summarised and tabulated by visit and time point. Pharmacokinetic coefficients, including but not limited to, maximal and minimal concentration, area under the concentration curve and, if possible, elimination half-life will also be summarised and tabulated with change from Baseline by visit.

Body mass index (BMI), waist circumference and waist:hip ratio with change from Baseline will be summarised and tabulated by visit and treatment group.

HbA1c, glucose and homeostatic model assessment of insulin resistance (HOMA-IR) will be summarised and tabulated with change from Baseline by visit and treatment group.

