Serum lipid profile values of total cholesterol, triglycerides and high and low density lipoproteins with change from Baseline and number of clinically significant values will be summarised and tabulated by visit and treatment group. Liver function values of ALT, AST, GGT, bilirubin and albumin, with change from Baseline will be summarised and tabulated by visit and treatment group. These liver function tests will also be correlated with HFF, CRP, and A1c. The proportion of subjects with ALT within the normal reference range at Week 24 will be summarised and tabulated by treatment group. Logistic regression modelling will be used to compare proportions in the Placebo group against each of the IMM-124E treatment dose groups using the same model used in the primary efficacy analysis, although the Baseline value of the liver function analyte will be used as a covariate. The area under the curve for change

from Baseline to Week 24, using the Baseline value as reference, for liver enzymes ALT, AST and GGT will also be analysed. For patients in the FAS population who withdraw prior to Week 24, the area under the curve will be adjusted in a manner comparable to a full 24 week period value.

The proportion of subjects demonstrating a decrease in liver percent fat at 24 weeks compared to baseline of 5%, 10%, 20% and 30% respectively will also be analysed. In a similar manner, proportional decreases in ALT, AST and A1c will be assessed using appropriate percentages.

Correlations between change in hepatic fat fraction and changes in ALT, C-reactive protein and A_{1c} will also be calculated.

The Fibrosis-4 Score will be calculated at each visit for which there is data. The formula is $FIB-4 = (Age * AST) / (Platelets / \sqrt{ALT})$. This score will be summarised and tabulated in the same manner as the primary endpoint.

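### SAP 7.3 names no model for the ALT, AST and GGT AUC of change; read through its default, the model leaves out the Baseline enzyme and gives up precision

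*SAP*

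**What the plan says.** SAP 7.3 introduces the enzyme AUC in one sentence: an area-under-the-curve summary of change taken "from Baseline to Week 24, using the Baseline value as reference, for liver enzymes ALT, AST and GGT will also be analysed". No model is attached to it.

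The general rule at the start of SAP 7.3 is that "inferential statistical analysis will be performed on the same basis as for the primary endpoint". SAP 7.2 analyses the primary change score by analysis of variance, "where the model will include the treatment group and another subgrouping variable". The candidate subgrouping variables are all categorical; one is baseline ALT cut at 1.5 times the upper normal limit.

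The SAP writes in a baseline covariate twice:

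- For values with three or more time-points, "the baseline value will be included in the repeated measures analysis as a covariate".
- For the logistic comparison of the proportion with normal ALT, the primary model is used, "although the Baseline value of the liver function analyte will be used as a covariate". This comes directly before the AUC sentence.

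The protocol synopsis (sample size determination) describes the primary model differently, as a "linear model that incorporates the baseline measure as a covariate, the stratification factor and randomized treatment group".

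The SAP table list (section 12) has AUC tables for each enzyme with no factor, and others with one categorical factor each, including the ALT category. None names the Baseline enzyme as a covariate.

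**The concern.** The AUC of change is one number per subject. It is not a repeated-measures outcome and not a binary one, so neither of the SAP's two baseline-covariate sentences reaches it. Read through SAP 7.2, it is compared between arms without the continuous Baseline value of the enzyme.

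Subtracting Baseline does not adjust for it. A subject with a high entry value tends to fall and one with a low entry value tends to rise, so the AUC of change is negatively correlated with Baseline. That predictable variation stays in the error term unless Baseline is in the model.

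Baseline enzymes are not randomisation factors (Protocol 8.1). Amendment 3 also aimed to improve recruitment by "eliminating the ALT eligibility requirement and using ALT as a secondary endpoint instead of a primary endpoint", so entry criteria no longer restrict the spread of Baseline ALT. What is at stake is the precision of a SAP analysis that supports the secondary objective on liver function.

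**Working it through.** **The plan's own figure.** The documents state power only for liver fat. SD of change = 6 × √(2 × (1 − 0.25)) = 7.35, given as 7.3. With 40 per arm, a difference of 5, SD 7.3 and two-sided 0.05, the t-test has 85.7% power, which agrees with the stated value of about 85%. No SD, correlation or power is given for ALT, AST, GGT or their AUCs.

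**Inputs for the AUC.** From the documents: 40 per arm, two-sided 0.05, and enzyme visits at Baseline and Weeks 1, 2, 4, 8, 12, 16, 20 and 24 (Protocol Table 1). Assumed: trapezoid AUC, equal variances, one correlation r between all visits, normality, complete data, and an effect that gives 80% power unadjusted.

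**Variance ratio.** The trapezoid weights in weeks are 0.5, 1, 1.5, 3, 4, 4, 4, 4 and 2, which sum to 24. Subtracting Baseline makes its weight 0.5 − 24 = −23.5, so the weights c now sum to zero. With unit variances:

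- Var(AUC of change) = (1 − r) × Σc²
- Cov(AUC of change, Baseline) = (1 − r) × c₀
- Adjusted variance = Var − Cov²
- Ratio = 1 − (1 − r) × c₀² / Σc²

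Here c₀² = 552.25 and Σc² = 552.25 + 1 + 2.25 + 9 + 4 × 16 + 4 = 632.5. The ratio is therefore 1 − 0.873 × (1 − r). The correlation of the AUC of change with Baseline is −√(0.873 × (1 − r)), which is −0.66, −0.51 and −0.30 at r = 0.5, 0.7 and 0.9.

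**Power with the covariate** = Φ((1.960 + 0.842)/√ratio − 1.960).

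**Partial adjustment from a binary split.** Under normality, a split with upper fraction q captures φ(z)²/(q(1 − q)) of the variance that Baseline explains. This is 0.637 at a median split and 0.490 at 80/20. The ratio becomes 1 − share × (1 − ratio).

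| Assumed r | Variance ratio | Power, continuous Baseline | Power, median split | Power, 80/20 split |
|---|---|---|---|---|
| 0.5 | 0.563 | 96% | 91% | 88% |
| 0.7 | 0.738 | 90% | 87% | 85% |
| 0.8 | 0.825 | 87% | 84% | 83% |
| 0.9 | 0.913 | 83% | 82% | 82% |

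The unadjusted power is 80% in every row. The split columns apply to ALT only, because the ALT category is not AST's or GGT's own baseline. At r = 0.7 the adjusted analysis needs about 40 × 0.738 ≈ 30 per arm for the unadjusted precision.

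**Sensitivity.** Dropping the Week 1 and Week 2 visits changes the adjusted power by less than one point. At the SAP's final alpha of 0.04695, unadjusted power is 79.2%, and on the Week 4 to 24 visits adjusted power is 95.6% (r = 0.5) to 82.7% (r = 0.9). Borrowing the liver-fat value r = 0.25 would give a ratio of 0.345 and 99.8%, but nothing in the documents supports that value for enzymes, so I do not rely on it.

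**The case against.** The strongest reply is that the omission is inferred. The AUC sentence gives no model, and the protocol's primary model does contain the baseline measure, so the same basis could be read as already including it. The sample tables in the SAP also have a row for an adjusted change, without saying what it is adjusted for. This stands as far as it goes: the documents show an unspecified model, not a stated decision to exclude Baseline. But the SAP's own primary model has no such term, and its logistic sentence presents the covariate as a departure from that model. A clarifying sentence is needed on either reading.

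The AUC is also supplementary. Protocol 4.2 lists mean enzyme changes by visit and ALT proportions, not an enzyme AUC. The visit-wise enzyme changes already receive Baseline as a covariate through the repeated-measures rule, and normal ALT receives it through the logistic model. That stands, and it limits the importance of the point.

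The tables by ALT category adjust the ALT AUC in part. That stands for ALT, but not for AST or GGT.

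Four stronger readings are tempting and not supported:

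- That the SAP confines the baseline covariate to repeated-measures models. The logistic sentence contradicts this.
- That the AUC falls under the rule "For analyses with only a baseline and final value, t-tests or Wilcoxon rank-sum tests will be performed". The enzymes are measured at up to nine visits, so that rule does not apply to their AUC.
- That the enzyme AUCs are the protocol's chosen measures for the liver-function objective. They are a SAP addition.
- That the comparison is biased. Under randomisation it is unbiased, and chance imbalance is already reflected in its variance.

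**Conclusion.** The point holds as a minor one. SAP 7.3 leaves the AUC model open, and its default leads to an ANOVA of change without the Baseline enzyme. The consequence is lost precision in a supplementary analysis of a trial that the protocol calls exploratory.

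Across assumed correlations of 0.5 to 0.9 the covariate raises power by roughly 16 down to 3 points from an 80% base, and no value in that range shows a loss. For ALT, the gain beyond what the category tables offer is smaller: about 5 points at r = 0.5 and 1 at r = 0.9 if the cut lies near the median, and more if it does not.

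These figures rest on a common between-visit correlation that the documents do not give, on normality and on complete data. Skewed enzyme values, or the SAP's undefined adjustment of the AUC for early withdrawals, could change them.

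**What to change.** In SAP 7.3, state that the AUC of change for each of ALT, AST and GGT is analysed by ANCOVA with treatment, the Baseline value of the same enzyme as a continuous covariate and the randomisation strata of Protocol 8.1. Add that a transformation or a rank-based version with the same covariate is used if the values are skewed. Settle this before unblinding.

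The cost is one sentence and one model term. Baseline ALT, AST and GGT are already in the Day 0 chemistry panel, so no new data are needed.

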##### Liver function:

- Mean change from Baseline in serum ALT, AST, bilirubin, albumin and GGT at Weeks 4, 8, 12, 16, 20 and 24
- Proportion of subjects whose ALT at Week 24 is within reference range defined a  $\leq 19$  IU/L for women and  $\leq 30$  IU/L for men
- The proportion of subjects demonstrating a decrease in serum ALT at 24 weeks compared to baseline equal or greater than 30% compared to placebo

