**Table 3: Safety Laboratory Parameters**

Test	Parameters
Hematology (Screening, Baseline, D7, D14, W4 and 4 weekly thereafter)	Hemoglobin, hematocrit, red blood cell (RBC) and RBC morphology, white blood cell (WBC) and differential WBC count, platelet count, mean corpuscular volume (MCV), mean corpuscular hemoglobin concentration (MCHC) and neutrophil count.
Coagulation (Screening, Baseline, D7, D14, W4 and 4 weekly thereafter)	Prothrombin time (PT), partial thromboplastin time (PTT), and International Normalized Ratio (INR).
Clinical Chemistry (Screening, then fasting at Baseline, D7, D14, W4 and 4 weekly thereafter)	Sodium, potassium, chloride, bicarbonate, blood urea nitrogen, creatine phosphokinase, creatinine, total protein, albumin, serum amylase (fractionated if > upper limit of normal (ULN)), lipase, phosphate, GGT, AST, ALT, alkaline phosphatase, total bilirubin, calcium, uric acid, glucose and insulin. CRP and C-peptide will be included at Baseline, W4, W12 and W24 only.
Serum lipid panel (Baseline, D7, D14, W4 and 4 weekly thereafter)	Total cholesterol, triglycerides, high and low density lipoproteins
Blood glucose (average) (Screening, W12 and W24)	HBA1c
Urine (Screening only)	Specific gravity, protein, glucose, blood, leukocytes, pH, ketones, bilirubin, urobilinogen, nitrites

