3.3 General statistical methodology

Treatment groups will be described as '600 mg IMM-124E', '1200 mg IMM-124E' and 'Placebo'. All tables, figures and listings will be produced for these three treatment groups. In addition, where specified, tables will be produced where subjects are grouped by baseline hepatic fat fraction, baseline HbA1c, and with a binary classification (not treated vs. treated).

General descriptive statistics for continuous measures will include number of observations (n), mean, standard deviation (SD), median, quartiles, minimum and maximum. For categorical variables, descriptive statistics will include n and percentage occurrence within the treatment group. The denominator for calculating percentage will be the number of valid observations within the treatment group.

For the basic and interim analysis, missing data will remain missing and not be imputed. However, for sensitivity measures in the final study analysis, missing values will also be imputed using a multiple imputation technique (Berglund, 2010 and Yuan, 2011).

This is a multicentre study, but no analysis using centre as a stratification factor will be performed, except for the primary endpoint, in which case the analysis will be performed on the imputed data both with and without centre as a stratification factor as a sensitivity analysis on the primary endpoint. Analysis of centre as a stratification factor will also be performed on ALT, AST, Glucose, A_{1c}, lipid profile parameters and CK-18.

Concomitant medications will be coded using the most recently available version of the World Health Organisation Drug Dictionary (WHO DD) at the time of data lock. Medications will be summarised and tabulated using the first and second levels of the dictionary. Medical history and adverse events will be coded using the most recently available version of the Medical Dictionary for Regulatory Affairs (MedDRA) at the time of data lock. Both medical history and adverse events will be summarised and tabulated using System Organ Class and Preferred Terms.

Patients given the wrong treatment will be analysed as randomised for efficacy measures (for the ITT, PP and FAS populations) and as treated for safety measures (Safety population and ET subgroup).

For safety data, if there are unscheduled visits where data values exist and those data are missing for the prior, scheduled, visit, then the values from the unscheduled visit will be imputed.

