Hepatic fat fraction with HbA1c sub-groups as stratification factor (FAS population)

Hepatic fat fraction with HbA1c sub-groups as stratification factor (PP population)

Hepatic fat fraction with Inflammation sub-groups as stratification factor (ITT population)

Hepatic fat fraction with Inflammation sub-groups as stratification factor (FAS population)

Hepatic fat fraction with Inflammation sub-groups as stratification factor (PP population)

Hepatic fat fraction with ALT sub-groups as stratification factor (ITT population)

Hepatic fat fraction with ALT sub-groups as stratification factor (FAS population)

Hepatic fat fraction with ALT sub-groups as stratification factor (PP population)

Hepatic fat fraction with outliers excluded (ITT population)

Hepatic fat fraction with outliers excluded (FAS population)

Hepatic fat fraction with outliers excluded (PP population)

ALT area under the curve values for 24 weeks of treatment (ITT population)

ALT area under the curve values for 24 weeks of treatment (FAS population)

ALT area under the curve values for 24 weeks of treatment (PP population)

ALT area under the curve values for 24 weeks of treatment with hepatic fat fraction sub-groups as stratification factor (ITT population)

ALT area under the curve values for 24 weeks of treatment with hepatic fat fraction sub-groups as stratification factor (FAS population)

ALT area under the curve values for 24 weeks of treatment with hepatic fat fraction sub-groups as stratification factor (PP population)

ALT area under the curve values for 24 weeks of treatment with HbA1c sub-groups as stratification factor (ITT population)

ALT area under the curve values for 24 weeks of treatment with HbA1c sub-groups as stratification factor (FAS population)

ALT area under the curve values for 24 weeks of treatment with HbA1c sub-groups as stratification factor (PP population)

ALT area under the curve values for 24 weeks of treatment with Fibrosis sub-groups as stratification factor (ITT population)

ALT area under the curve values for 24 weeks of treatment with Fibrosis sub-groups as stratification factor (FAS population)

ALT area under the curve values for 24 weeks of treatment with Fibrosis sub-groups as stratification factor (PP population)

ALT area under the curve values for 24 weeks of treatment with Ballooning sub-groups as stratification factor (ITT population)

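### SAP 7.3 gives no rule for turning an early leaver's liver-enzyme AUC into a 24-week value, and either natural rule understates a change that is still building

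*SAP*

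**What the plan says.** SAP 7.3 summarises the enzyme course as an AUC of changes: "from Baseline to Week 24, using the Baseline value as reference, for liver enzymes ALT, AST and GGT will also be analysed". When an FAS subject withdraws before Week 24, "the area under the curve will be adjusted in a manner comparable to a full 24 week period value". It gives no formula, no minimum follow-up and no sensitivity analysis for this step.

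Three other provisions bear on it:

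- SAP 3.3: "For the basic and interim analysis, missing data will remain missing and not be imputed". It adds that "for sensitivity measures in the final study analysis, missing values will also be imputed using a multiple imputation technique", but the table list in SAP 12 names multiple imputation only for hepatic fat fraction.
- SAP 7.3, for variables with three or more time points: "the baseline value will be included in the repeated measures analysis as a covariate".
- Protocol 4.2 defines the enzyme endpoint by visit: "Mean change from Baseline in serum ALT, AST, bilirubin, albumin and GGT at Weeks 4, 8, 12, 16, 20 and 24". The AUC is an addition made in the SAP.

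Protocol Table 3 sets the fasting chemistry samples at Baseline, then "D7, D14, W4 and 4 weekly thereafter". SAP 12 lists the enzyme AUC tables for the FAS, ITT and PP populations, overall and by six subgroup factors.

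**The concern.** The curve is change from Baseline, so it starts at zero. A subject who leaves early contributes only the first part of it. Whatever converts that part to a 24-week value lets early weeks stand in for weeks that were not observed. If the enzyme falls gradually, the early weeks hold less of the fall, and the converted value is too close to zero. The analysis then treats it as if it had been observed.

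The error depends on when and how often subjects leave. An arm with more or earlier leavers would look less improved than an arm with the same true course. SAP 7.3 also leaves the choice of rule open, so it could be made after the data are seen.

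**Working it through.** The documents give no figure for the enzyme AUC, no expected enzyme course and no withdrawal rates by arm. There is therefore no stated figure to reproduce. The courses and rates below are assumptions, shown as a range.

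**Inputs.** Sampling at weeks 0, 1, 2, 4, 8, 12, 16, 20 and 24 (Protocol Tables 1 and 3). Assumed change at Week 24: -20 IU/L. Both arms share the same true course, so any arm difference is false.

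**One leaver, 24/t reading, linear course** (change = -20 × t/24).

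- Completer: -20 × 24/2 = -240 IU·wk/L.
- Leaver at week T: AUC to T is -20 × T²/48, then multiplied by 24/T.
- T = 4: -6.67 × 6 = -40 (17% of -240).
- T = 8: -26.67 × 3 = -80 (33%).
- T = 12: -60 × 2 = -120 (50%).

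**One leaver, 24/t reading, change complete by Week 4** (linear to -20, then flat).

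- Completer: -40 - 400 = -440.
- T = 4: -40 × 6 = -240 (55%).
- T = 8: (-40 - 80) × 3 = -360 (82%).

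**One leaver at Week 8, last value extended.**

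- Linear: -26.67 + 16 × (-6.67) = -133, against -240.
- Change complete by Week 4: -120 + 16 × (-20) = -440, no error. This reading fails only if the change is still building at withdrawal.

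**Arm difference, 20% versus 5% leaving at Week 8, 24/t reading.** The false difference is (0.20 - 0.05) × (completer value - leaver value).

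- Linear: 0.80 × (-240) + 0.20 × (-80) = -208, against 0.95 × (-240) + 0.05 × (-80) = -232. The difference is 24, and 24/240 = 10%.
- Change complete by Week 4: 0.15 × 80 = 12, and 12/440 = 2.7%.
- Equal rates and timing, or no mean change: zero.

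Extending the last value under the linear course gives 0.15 × (240 - 133.3) = 16, and 16/240 = 6.7%.

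**Larger imbalance.** At 30% versus 10% leaving at Week 8 with 24/t scaling, the false difference is 13.3% of the AUC (linear), 8.1% (half-time of four weeks) or 0.9% (complete by Day 7).

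**Effect on error rate.** This was simulated with 24/t scaling, 40 per arm, 4,000 replicates and a two-sample t-test at nominal 5%. Further assumptions were a mean fall of 20 U/L, between-subject response SD 12, visit SD 10, and withdrawal at Weeks 4 and 8 unrelated to outcome. Monte Carlo SE is about 0.3 to 0.5 points.

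| Course | 30% vs 10% leave | 40% vs 10% leave |
|---|---|---|
| Linear | 7.4% | 12.4% |
| Half-time four weeks | 8.3% | 11.8% |
| Complete by Day 7 | 5.5% | 4.8% |

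With a fall of 10 U/L and 30% versus 10%, the rates are 6.3% (linear) and 6.1% (half-time four weeks). With no mean change they stay near 5%. For the courses in the table, the completers-only comparison in the same runs also stayed near 5%.

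**Tables affected.** 3 enzymes × 3 populations × (overall + 6 subgroup factors) = 63. The 21 PP tables hold only subjects who completed 24 weeks (SAP 3.1). The 21 FAS tables include early leavers, as would the 21 ITT tables. SAP 3.1 has the ITT population tested only if someone was randomised but untreated.

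**The case against.** The strongest reply is that SAP 7.3 does not say how it adjusts, so no biased rule is actually stated. That is right, and the missing formula is the firmer half of the point. It does not dispose of the rest, because both natural readings misstate a change that is still building.

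Next, the size rests on assumed courses and rates. This stands: a fast plateau leaves little error, and an imbalance in withdrawal is not enough without a changing mean.

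Third, little depends on the AUC. It is a secondary summary added in the SAP to a trial that Protocol 12 calls exploratory. The same enzymes are analysed by visit, and the PP tables already give a view free of the adjustment. This stands and limits the harm. However, PP subjects are a selected group, and no listed table tests the adjustment in the FAS.

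Fourth, SAP 3.3 is a general rule and SAP 7.3 a specific one. A value scaled by 24/t is the time-averaged change over the observed weeks multiplied by 24, so it fills in no visit. That is a fair defence of the wording, which needs reconciling but is not a flat contradiction. As a 24-week value, though, it is comparable with a completer's only if the average change over the observed weeks equals that over all 24.

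Finally, a model-based AUC is not free. SAP 7.3 puts secondary analyses on the same basis as the primary, including the rank and permutation fallbacks of SAP 7.2, and model visit means are not available under those. This also stands and is met in the fix.

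**Conclusion.** The point holds in a limited form. The adjustment is undefined, it sits badly with SAP 3.3, and under either natural reading it biases an early leaver's AUC toward zero when the change is still building. A false arm difference needs two things together: a mean change that is not constant over the 24 weeks, and withdrawal rates or timing that differ between arms. On the assumptions shown (20% versus 5% leaving at Week 8, 24/t scaling), it runs from 2.7% to 10% of the AUC.

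A reader might infer that the SAP scales by 24/t, that unequal withdrawal alone creates a false effect, or that all three populations are affected. The documents support none of these. No scaling rule is written, the error vanishes when there is no mean change, and the PP tables contain no early leavers. Nor do the documents show that withdrawal will be unequal.

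This is a worthwhile correction to a secondary summary. It does not touch the primary endpoint. The simulation takes withdrawal as unrelated to outcome; withdrawal driven by enzyme values could add bias in either direction.

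**What to change.** Replace the adjustment sentence in SAP 7.3. Make the main AUC comparison a linear combination of visit means from the repeated-measures model already planned there, with Baseline as covariate, a treatment-by-visit term and all observed visits of FAS subjects. Report dose-versus-placebo contrasts. On the protocol's visit grid the trapezoid weights are 1 (week 1), 1.5 (week 2), 3 (week 4), 4 each (weeks 8, 12, 16 and 20) and 2 (week 24). Applied to the linear course these return -240. Use the PP AUC tables already listed as the check in completers.

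If subject-level AUCs are kept, for example for the rank or permutation fallback, derive them from multiply imputed visits. Otherwise state the formula and a minimum follow-up, and label the result as sensitivity only. A minimum matters because 24/t would multiply a Day 7 leaver's AUC by 24. Reconcile the text with SAP 3.3. Say also whether withdrawal means from treatment or from the study, and how ongoing subjects with partial follow-up are handled at the interim (SAP 9).

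The cost is SAP wording, a stated treatment-by-visit term and covariance structure, and one added contrast per enzyme and dose. The main analysis then relies on missing at random and gives no individual AUC for early leavers.
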